### **10.4. Management of Administrative Data**

REDCap will be used to facilitate the flow of information and increase the level of communication between MyNewOptions research team members and participants. In addition, a shared, password protected server will be used to maintain research records including all meeting agendas and minutes; IRB documents and status reports; participant communication and payment records; copies of abstracts, manuscripts and presentations; and any other pertinent study information.

## 11. Statistical Consideration

### 11.1. Introduction and Aims

MyNewOptions is a randomized controlled trial designed to test interventions for assisting privately insured women to formulate and achieve their reproductive goals and avoid unintended pregnancy.

- **The primary aim** is to assess whether women in the RLP and RLP+ intervention groups are more likely to use contraception when not intending pregnancy than women in the control group. Secondary outcomes include effectiveness of contraceptive methods chosen, method satisfaction, and contraceptive self-efficacy.
- **The secondary aim** is to assess whether women in the intervention groups have more continuous contraceptive use and contraceptive adherence over a two-year follow-up period than women in the control group.

### 11.2. Analysis Plans

#### 11.2.1. Primary Outcome Variable (Aim 1)

##### 11.2.1.1. Contraceptive use

Using standard measurement, participants will be asked at each assessment if they are currently doing anything to prevent pregnancy (Y/N). The primary outcome measure for Aim 1 will be the proportion of 6-month intervals women are reporting any contraceptive use out of the number of 6-month intervals women are not intending pregnancy. Duration of contraceptive method use will also be assessed. Whether any contraception is being used is defined as a binary variable (yes/no) at each 6-month interval post-baseline (6, 12, 18, and 24 months). We will construct a proportion for each participant as the number of time periods in which the participant is using contraception, divided by the number of time periods in which the participant is not intending pregnancy.

#### 11.2.2. Secondary Outcome Variables (Aim 1)

##### 11.2.2.1. Contraceptive method effectiveness

If women are using a method of contraception, the type of contraception will be identified. Contraceptives will be classified into groups based on known efficacy, determined by published typical failure rates, as shown in Table 2. Contraceptive efficacy will be measured ordinally as: no method, less effective methods, more effective methods, and most effective methods.

**Table 2.** Categorization of contraceptive efficacy

Method	Typical-use failure rate in 1 st year
No method	85
Less Effective Methods	
Withdrawal	22
Fertility-awareness methods	24
Condom (female)	21
Condom (male)	18
More Effective Methods	
Oral contraceptives	9
Evra patch	9
NuvaRing	9
Depo-Provera	6
Most Effective Methods	
IUD—copper T	0.8
IUD—Mirena	0.2
Contraceptive implant	0.05
Sterilization (female)	0.5
Sterilization (male)	0.15

### 11.2.2.2. Satisfaction with contraceptive method

A validated 5-item contraceptive satisfaction measure will be used that measures satisfaction with ease of use, effectiveness, side effects, cost, and overall satisfaction. Additional validated items will be included to indicate satisfaction with partner support of the contraceptive method.

### 11.2.2.3. Contraceptive self-efficacy

We developed and pilot tested a 9-item contraceptive self-efficacy scale for adult women for the purposes of this study. While a validated scale to measure contraceptive self-efficacy in adolescents exists, it was not applicable for adult women. Pilot testing indicated good internal reliability with a Cronbach's alpha of 0.78.

## 11.2.3. Primary Outcomes Variables (Aim 2)

### 11.2.3.1. Continuity of Contraceptive Use and Adherence

Continuity of contraceptive use describes whether women use contraception continuously, or have periods where they stop using contraception while at risk for pregnancy. Items will assess contraceptive method use throughout the preceding 6 months to determine episodes of contraceptive use, gaps in contraceptive use, and risk for pregnancy during gaps in use. Contraceptive continuation over each 6-month assessment interval will be measured using an ordinal longitudinal contraceptive use typology as described by Frost and colleagues: 1) continuous contraceptive users of one method, 2) continuous users with at least one method switch, 3) non-continuous users with gaps in use when not at risk for pregnancy, 4) non-continuous users with gaps in use when at risk for pregnancy, and 5) continuous nonusers. This typology has been shown to be associated with risk for unintended pregnancy.

### 11.2.3.2. Contraceptive adherence

Contraceptive adherence will be classified as high, medium, and low using self-report and pharmacy claims data, depending on the type of contraception being used. For women who have had a sterilization procedure (male or female) or LARC initiation since study enrollment, adherence will be categorized as high. For coital-dependent methods, standard self-reported adherence measures will be used to define adherence categories as shown in Table 3.

Table 3. Definition of Contraceptive Adherence

Methods	Measurement	Definitions	Adherence Category
Sterilization or LARCs (i.e., IUD, contraceptive implant)	Self-report	Adherence assumed	High
Coital dependent methods (i.e., spermicides, withdrawal, sponge, condoms, diaphragm, fertility awareness methods)	Self-report: What percent of time did you use your birth control method during sex in the past 6 months?	Always (100%)	High
		Most of the time (71-99%)	Medium
		Often (51-70%)	
		Sometimes (31-50%)	Low
		Occasionally (1-30%)	
Never (0%)			
Oral contraceptives, contraceptive patch, contraceptive ring, DMPA	Pharmacy claims data: Medication Possession Ratio	MPR >90%	High
		MPR 80-90%	Medium
		MPR <80%	Low

While self-report measures of oral contraceptive adherence have been the standard in research of this type, self-report has been poorly validated against electronic medication monitors and biochemical assays of medication metabolites. In light of this, we will measure adherence to prescribed contraceptives (i.e., oral contraceptives, patch, shot (DMPA), or ring) using *pharmacy claims data* through Highmark to determine medication possession ratios (MPR). The MPR is the sum of days supply for all prescription fills in the study period, divided by the number of days in the study period. Using pharmacy claims data in this manner can help characterize poor adherence to prescribed medications, including hormonal contraceptives. Since direct observation of medication use is not possible in this study, acquisition of timely refills serves as an appropriate surrogate. Medication adherence has generally been accepted to be an MPR>80%, however this is likely too low when studying contraception. Thus, we will define high (MPR>90%), medium (80-90%), and low adherence (<80%) categories. Highmark preliminary data shows that 6% of members disenroll annually. For participants who are no longer enrolled in Highmark, we will be unable to obtain MPR data for prescription contraceptives. In those cases we will use retrospective self-report measures on contraceptive compliance over the past 6 months. A recent study shows that retrospective report of oral contraceptive use in this manner is equivalent to prospective medication diaries.

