##### 3.1.2. Secondary Hypotheses

Compared with random assignment to an information only control group, random assignment to a reproductive life planning tool (RLP) or a reproductive life planning tool plus a contraceptive action planning tool (RLP+) will:

- Lead to the use of more effective contraception
- Result in more continuous use and better method adherence during the two year study period.
- Improve contraceptive method satisfaction
- Result in lower rates of unintended pregnancy (exploratory outcome)

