**7.3. Reproductive Life Planning Intervention plus Action Planning (RLP+)**

The Reproductive Life Planning Plus (RLP+) intervention is the RLP intervention described above plus an additional *action planning* step with the objective of improving contraceptive adherence. Action planning interventions (also known as “if-then planning,” “implementation intentions,” or “contingency planning”) are based on self-regulation, defined as a “goal-guidance process, occurring in iterative phases, that requires the self-reflective implementation of various change and maintenance mechanisms that are aimed at task- and time-specific outcomes.” While action planning interventions vary, they tend to have several elements in common. First, they present participants with common situations that make it difficult to perform a behavior. Second, they ask participants to make a specific plan for what they will do when faced with the specific situational barrier (i.e., “If situation X is encountered, then I will initiate goal-directed behavior Y.”). By specifying when, where, and how one will act, action planning passes control of behavior to future environmental cues, reducing the need for cognitive control and effort. A common design for these interventions is the use of a worksheet that has two columns—the left column lists the difficult situations and the right column lists the actions to overcome the difficult situation. Users are then asked to identify the difficult situations they may encounter, and then “link” the situation to an action that they will now be prompted to do if they encounter the situation. An example from our oral contraceptive action planning tool is shown below in Figure 1.

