### 11.3. Analytic Methods

#### 11.3.1. Specific Aim 1

The outcome variables are binary (contraception use; satisfied with contraceptive method) and ordinal (contraceptive method effectiveness), and will be measured at four time periods post-baseline (6, 12, 18, and 24 months). For the binary outcome variables, we will construct a proportion for each participant as the number of time periods in which the participant's response is positive, divided by the number of time periods in which the participant is not intending pregnancy. The denominator will be four, except for those participants who withdraw consent from the study, change their minds about intending pregnancy during the study, or become pregnant. Therefore, we will apply a binomial regression analysis to these proportions. We will use intervention group assignment (intention-to-treat analysis) as the sole regressor in the primary analysis, but we will investigate in secondary analyses the effects of selected covariates on the proportional response (demographics; pregnancy history; sexual and contraceptive history; perceived control/fatalism toward contraception; relationships; compliance with log-in requirements). In terms of the three randomized groups, we will construct two-sided test statistics for comparing: 1) RLP to control, 2) RLP+ to control, and 3) RLP to RLP+. Therefore, we will impose a Bonferroni correction factor to the significance level ( $\alpha = 0.0167$ ). We will apply additional secondary analyses that are longitudinal, in which we invoke a logistic regression model with random participant effects to investigate if there are any time period effects and/or time period by intervention interactions for the binary outcomes. Finally, we will invoke a shared parameter model to account for the informative censoring that could occur due to participant withdrawal in a longitudinal study. In our setting, the shared parameter model includes a Weibull time-to-event regression model for the time to participant withdrawal in conjunction with a logistic regression model with random participant effects for the binary outcome.

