For the ordinal outcome variable of contraceptive method, we will code it for each participant as 0 (no method), 1 (less effective method), 2 (more effective method), or 3 (most effective method), and we will construct an average score for each participant across those time periods in which the participant is not intending pregnancy. We will apply a weighted regression analysis to these average scores, in which the weighting factor for a participant is the variance of her estimated average. Then the statistical analysis will proceed in a similar manner to that described above for the binary outcomes, and we will embed an ordinal logistic regression model with random participant effects to investigate if there are time period effects and/or time period by intervention interactions.

[figure not shown]
#### 11.3.2. Specific Aim 2

The outcome variables are ordinal (continuity of contraceptive use; contraceptive adherence), and will be measured at four time periods post-baseline (6, 12, 18, and 24 months). For the contraceptive continuation, we will code it for each participant as 0 (continuous non-use), 1 (non-continuous use with gaps when at risk for pregnancy), 2 (non-continuous use with gaps when not at risk for pregnancy), 3 (continuous use with at least one method switch), or 4 (continuous use of one method). For the contraceptive adherence variable, we will code it for each participant as 0 (none), 1 (low), 2 (medium), or 3 (high). We will analyze these ordinal outcomes in the same manner as described above for the ordinal outcome in Specific Aim 1.

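### The Aim 2 adherence score mixes any use, method class and adherence within a method, so it can differ between arms when only use or method choice has changed

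*Protocol*

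**What the plan says.** Adherence is one of the two outcome variables of Aim 2. Section 11.2.3.2 defines three levels: "Contraceptive adherence will be classified as high, medium, and low using self-report and pharmacy claims data". Coital-dependent methods are graded by self-report, and pill, patch, ring and injection by medication possession ratio. For the remaining methods nothing is measured: "For women who have had a sterilization procedure (male or female) or LARC initiation since study enrollment, adherence will be categorized as high". Table 3 gives the same high grade to sterilisation and LARC as assumed, with no condition on when the method was started.

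Section 11.3.2 uses four levels: "For the contraceptive adherence variable, we will code it for each participant as 0 (none), 1 (low), 2 (medium), or 3 (high". It then refers back to Aim 1: "We will analyze these ordinal outcomes in the same manner as described above for the ordinal outcome in Specific Aim 1". There, "we will construct an average score for each participant across those time periods in which the participant is not intending pregnancy", and the analysis otherwise follows the one for the binary outcomes: "We will use intervention group assignment (intention-to-treat analysis) as the sole regressor in the primary analysis". The average is weighted by the variance of each woman's estimated mean.

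The hypothesis in section 3.1.2 is "Result in more continuous use and better method adherence during the two year study period", listed separately from use of more effective contraception. Section 2.2 describes the aim as helping women adhere to the method they have chosen. Section 7.3 describes RLP+ as RLP with an added action planning "step with the objective of improving contraceptive adherence".

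**The concern.** Three different things move this score: whether a woman uses any method (if 0 means a period with none), whether she uses a method graded high by assumption, and how well she adheres to a method that depends on her own action. Only the third is adherence to a chosen method. The first is the primary outcome of the trial and the second is close to the method-effectiveness outcome of section 11.2.2.1. RLP is designed to prompt method choice, so arms may well differ on the first two.

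At stake is the wording of the Aim 2 conclusion. A significant result could be reported as better method adherence although no woman adhered better to any method.

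Two contradictions add to this. The number of levels differs between sections 11.2.3.2 and 11.3.2. The text of 11.2.3.2 also grants the high grade to LARC begun after enrolment, while Table 3 grants it to every LARC user.

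**Working it through.** **Plan's own figure.** The protocol gives no power or sample size for adherence. Its 324 per arm comes from the Aim 1 binary outcome: 0.25 versus 0.35 at two-sided 0.025 and 90% power needs 520 per arm; 520/4 periods = 130; 130/(1 − 0.60) = 325, which matches 324 closely. It enters below only as the number per arm.

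**Inputs.** From the protocol: scores 0 to 3, LARC and sterilisation = 3, group as sole regressor, 324 per arm, alpha 0.05/3 = 0.0167 (section 11.3.1; critical value 2.394). Assumed, because the protocol gives no method mix: control arm with 10% no method (scored 0), 10% LARC or sterilisation, 80% user-dependent methods split low/medium/high 30/25/45. This split is the same in both arms, so within-method adherence does not differ.

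**Formulas.** Let N be the share with no method and L the share on LARC or sterilisation.
- User-dependent mean = 0.30×1 + 0.25×2 + 0.45×3 = 2.15; mean square = 0.30×1 + 0.25×4 + 0.45×9 = 5.35.
- Arm mean = 3L + 2.15(1 − N − L).
- Arm variance = 9L + 5.35(1 − N − L) − mean².
- Difference between arms = 0.85 × (rise in L) + 2.15 × (fall in N).

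Control: mean 0.30 + 1.72 = 2.02; variance 0.90 + 4.28 − 4.0804 = 1.0996.

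**Results**, one fully correlated score per woman, no losses, z = difference / √((v₀ + v₁)/324):

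| Shift | Difference | Comparator variance | SE | z | Rejection | Range, user mixes 20/20/60 to 40/25/35 |
|---|---|---|---|---|---|---|
| None | 0 | 1.0996 | 0.0824 | 0 | 1.7% | 1.7% |
| LARC 10% to 15% | 0.0425 | 1.1086 | 0.0826 | 0.51 | 3.2% | 2.4–4.1% |
| LARC 10% to 20% | 0.0850 | 1.1140 | 0.0827 | 1.03 | 8.6% | 4.9–13.1% |
| LARC 10% to 30% | 0.1700 | 1.1139 | 0.0827 | 2.06 | 37% | 18–56% |
| No method 10% to 5% | 0.1075 | 0.9212 | 0.0790 | 1.36 | 15% | 12–20% |
| LARC 10% to 20% and no method 10% to 5% | 0.1925 | 0.9173 | 0.0789 | 2.44 | 52% | 48–56% |

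With 324 × 0.49 = 159 per arm (30% lost per year for two years), the combined shift still rejects 25%.

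**If 0 does not mean non-use** and non-users go unscored, 324 × 0.9 ≈ 292 users per arm remain. LARC 10% to 20% of all women is 11.1% to 22.2% of users: difference 0.0944, variances 0.718 and 0.691, SE 0.0695, z = 1.36, rejection 15%. LARC 10% to 30% is 11.1% to 33.3%: difference 0.189, variances 0.718 and 0.646, SE 0.0683, z = 2.76, rejection 64%. The LARC part does not need the inference about 0.

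**Four periods, 30% attrition per year (simulation, 1,500 replicates per scenario).**
- Weights equal to periods observed: 8% (LARC 10% to 20%), 37% (10% to 30%), 17% (no method 10% to 5%), 55% (combined).
- LARC uptake only from the third assessment, 10% to 20%: about 3%.
- Variance weights taken literally: women with a constant score get zero weight. Rejection is about 1–2% when uptake is early and unrelated to adherence, but 8% and 32% for the two LARC-only shifts when poor adherers are the ones who switch.
- Inverse-variance weights with a floor, uptake early and unrelated to adherence: 10–62% across the four shifts.

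**User-dependent methods only.** Rejection stays at about 0.015–0.025 when switching is unrelated to adherence. When poor adherers switch, it is about 26% (LARC 10% to 20%) and 73% (10% to 30%) with no within-method effect.

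**The case against.** The strongest reply is that the score measures what the protocol intends. Section 2.2 attributes poor adherence partly to methods that do not suit a woman's life, section 2.3 faults older trials for working on existing methods without asking whether they suited, and the action-plan excerpt in section 7.3 offers switching as one response. On that view a poor pill-taker who moves to an IUD has improved, and the assumed grade is stated openly. This stands as a defence of keeping the composite. It does not justify reporting a composite result as better adherence to the chosen method.

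The size is also open to attack, and most of that stands. Every shift is assumed, small LARC shifts do little, and literal weighting can largely remove the effect. That 0 means non-use is inferred from the averaging over all not-intending periods.

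Three stronger readings are tempting, and the documents support none of them:
- **That the test has an inflated type I error.** The randomised comparison is valid for the composite. The fault lies in the name and the interpretation.
- **That a high grade for LARC simply marks a switch after randomisation.** Only the text of 11.2.3.2 points that way; Table 3 covers all LARC users, and the text alone leaves women with LARC in place at enrolment without a grade.
- **That the hypothesis should be tested only in women on user-dependent methods.** That group is formed after randomisation. Section 7.2's own example is a pill user who misses pills and considers a more effective method, which is the selection that produced 26% and 73% above.

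**Conclusion.** The point holds as one of definition and interpretation. As written, the Aim 2 adherence score is a composite of any use, method class and within-method adherence, and a difference in the first two alone can produce a significant result well above the nominal 1.7%. Under the assumed mixes this runs from negligible (about 3% for a five-point LARC shift) to about half of trials (52% for the combined shift). The documents cannot say where in that range the trial will fall, and the weighting rule adds further uncertainty.

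The two scoring contradictions, three levels against four and new LARC against all LARC, rest on the text alone and need no assumption.

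**What to change.** In sections 11.2.3.2 and 11.3.2:

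1. Reconcile the number of levels: say whether 0 means a period with no method, or remove it.
2. Make the text and Table 3 agree on LARC already in place at enrolment.
3. Keep the score in all randomised women as the Aim 2 comparison, but name it a composite of use, method and adherence. Report by arm its components: non-use, LARC or sterilisation, and high/medium/low among user-dependent methods.
4. Add within-method adherence on user-dependent methods as a supportive analysis only, stating that the group is selected after randomisation and that the result can be biased if poor adherers switch.
5. State that a significant composite will not be described as better adherence to the chosen method unless the components support that reading.

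The cost is wording, some extra tabulation of data already collected, and a more cautious conclusion. No new data or participants are needed.

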## 6. Measures and Procedures

### 6.1. Informed Consent

Signed informed consent will not be required for participation in this study because the act of voluntarily participating in the online enrollment process is considered implied consent. However, participants will be required to check a box during the eligibility process assenting to the Summary Explanation of Research document, which will describe the study in detail including the rights of the research participant and potential risks associated with study participation. This document will inform potential participants that a Certificate of Confidentiality was requested and granted by the National Institutes of Health in order to protect the research team from being forced to share court ordered information about participants. Participants will also assent by checking a box to allow Highmark Health to provide the MyNewOptions study investigators with participant contraceptive pharmacy claims and health care utilization claims occurring 6 months prior to study enrollment through the end of the 2-year study period.

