### **8.2. Confidentiality**

There is potential risk for loss of confidentiality; participants will be informed that we will have attempted to minimize those risks by keeping all identifiable data in password protected electronic data files, that all data will be de-identified once data collection is completed, and that no participants will be identified in any analyses or reports. Data for this study will include: 1) self-administered computer surveys and 2) medical and pharmacy claims data abstracted from Highmark Health. Confidentiality of data will be maintained by assigning project-specific identification numbers to each participant for the purpose of linking the survey data with the abstracted claims data. Once the survey data are collected and linked with the clinical data abstracted from the registries, all identifying information will be destroyed, creating a de-identified dataset for analysis. This study has also applied for and received an NIH Certificate of Confidentiality.

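### For enrolled women, adherence to the injectable (DMPA) is scored from pharmacy fills alone, so injections billed as medical claims would be missed and a fully covered woman could be classed Low

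*Protocol*

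**What the plan says.** Table 3 in Section 11.2.3.2 puts four methods in one row, "Oral contraceptives, contraceptive patch, contraceptive ring, DMPA", with one measurement source, "Pharmacy claims data: Medication Possession Ratio". The text below the table names the injectable again: "we will measure adherence to prescribed contraceptives (i.e., oral contraceptives, patch, shot (DMPA), or ring) using" pharmacy claims. The ratio is defined there, with the length of the study interval as its denominator: "The MPR is the sum of days supply for all prescription fills in the study period, divided by the number of days in the study". On the cut-offs, "we will define high (MPR>90%), medium (80-90%), and low adherence (<80%) categories".

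One departure from claims is stated: "For participants who are no longer enrolled in Highmark, we will be unable to obtain MPR data for prescription contraceptives". Those women are scored by retrospective self-report. The same paragraph puts disenrolment at 6% a year.

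Section 11.3.2 codes adherence 0 (none), 1 (low), 2 (medium) or 3 (high) and measures it at 6, 12, 18 and 24 months.

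The trial also obtains claims other than pharmacy claims. Under Section 6.1 participants agree to release "participant contraceptive pharmacy claims and health care utilization claims occurring 6 months prior to study enrollment" up to the end of the two years. Section 8.2 lists among the study data "medical and pharmacy claims data abstracted from Highmark Health". Section 11.2.3.2 does not use the medical claims for adherence.

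**The concern.** DMPA is an injection. If it is supplied and given during a provider visit and billed as a medical claim, there is no pharmacy fill and nothing enters the numerator of the ratio. For an enrolled woman that gives a computable value of 0%, not a missing one, and Table 3 classes it as Low. The self-report route does not reach her, because it is reserved for women who have left the insurer. The same woman with the same coverage could be classed High by self-report after disenrolling and Low while enrolled.

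Section 11.2.3.2 justifies the ratio by treating timely refills as a surrogate for use. That surrogate fails where the product is not obtained by refill. For sterilization and long-acting methods Table 3 does not rely on fills and assumes High adherence. DMPA gets no corresponding allowance.

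The interventions are meant to influence method choice (Section 7.2), so the share of women using DMPA could differ between arms, and the error with it.

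**Working it through.** The protocol gives no figure to reproduce here. The check applies its own rule to a woman with no gap in coverage.

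**Inputs from the protocol.** MPR = (sum of days supply of fills) / (days in period). High is above 90%, Medium 80–90%, Low below 80%. Codes are High 3 and Low 1.

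**Assumptions, not in the protocol, used only for arithmetic.** Two injections in a 6-month period (182.5 days) or eight in 24 months (730 days). Each is credited with 84, 90 or 91 days. An injection billed as a medical claim leaves no pharmacy fill.

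**Step 1: one woman.** MPR = (injections filled at a pharmacy × days credited) / (days in period).

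| Period | Filled at a pharmacy | MPR (84 / 90 / 91 days) | Class |
|---|---|---|---|
| 6 months | 0 of 2 | 0% | Low |
| 6 months | 1 of 2 | 46.0 / 49.3 / 49.9% | Low |
| 6 months | 2 of 2 | 92.1 / 98.6 / 99.7% | High |
| 24 months | 6 of 8 | 69.0 / 74.0 / 74.8% | Low |
| 24 months | 7 of 8 | 80.5 / 86.3 / 87.3% | Medium |
| 24 months | 8 of 8 | 92.1 / 98.6 / 99.7% | High |

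For example, 1 × 84 / 182.5 = 46.0% and 2 × 84 / 182.5 = 92.1%. If medical injection claims are counted with pharmacy fills, she is High under all three day values and over both periods. When none of her injections is filled at a pharmacy, the coding error is 1 − 3 = −2 points. Section 11.3.2 also has a code 0 (none) that Table 3 does not define. If a ratio of 0% were given that code, the error would be −3.

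**Step 2: one arm's mean.** Shift = −2 × (DMPA share) × (share injected under medical claims). With assumed shares of 2–5% and 50–100%, this runs from −2 × 0.02 × 0.50 = −0.02 to −2 × 0.05 × 1.00 = −0.10. With wider assumptions of 2–10% and 25–100%, it runs from −0.01 to −0.20.

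**Step 3: the contrast between arms.** If the share injected under medical claims is the same in both arms, the size of the bias is 2 × (difference in DMPA share) × (that share). For an assumed 1-percentage-point difference:

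- 2 × 0.01 × 0.50 = 0.01 points
- 2 × 0.01 × 1.00 = 0.02 points

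The arm with more DMPA users is understated. With equal DMPA shares the bias is 0, and noise and some dilution remain.

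**Step 4: which method changes are distorted.** Take DMPA under medical claims as scored 1 and truly 3.

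| Change | Scored change | True change |
|---|---|---|
| None (0) to DMPA | +1 | +3 |
| Method scored low (1) to DMPA | 0 | +2 |
| Method scored medium (2) to DMPA | −1 | +1 |
| Method scored high (3) to DMPA | −2 | 0 |
| DMPA to a long-acting method (3) | +2 | 0 |

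A false fall or false gain arises only for changes between DMPA and methods scored medium or high. The first two rows are understated but do not reverse.

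**The case against.** The strongest objection is that the key premise lies outside the protocol. Nothing in it says where DMPA is given or how the insurer bills it. Section 5.1 restricts invitations to members with prescription coverage, so every invited woman has a pharmacy route, and where DMPA is filled at a pharmacy the rule works as written. This stands: the point is conditional, and no size can be derived from the protocol alone.

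A reader might infer that any movement towards or away from DMPA pushes the score the wrong way. The codes in Section 11.3.2 do not support that. Starting DMPA from no method still raises the score, and moving to it from a method scored low leaves the score unchanged.

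A reader might also take the 0.02–0.10 shift in an arm's mean as the trial's bias. It is not. The trial compares randomised arms, and a shift common to both largely cancels.

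It can be said, too, that claims coding belongs in a statistical analysis plan, which is not at hand. That carries limited weight, because Section 11.2.3.2 does not leave the source open. It names pharmacy fills, names DMPA and sets the cut-offs.

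**Conclusion.** The point holds in conditional form and is minor. For women still enrolled, the protocol fixes a pharmacy-only rule for DMPA and has no provision for injections that generate no fill. Assuming some injections are billed as medical claims, a continuously covered woman is scored 1 instead of 3. The bias in an arm contrast is about 0.01–0.02 points for a 1-percentage-point difference in DMPA share and a 50–100% share under medical claims. Both inputs are assumptions, and the figure also assumes that the affected women are truly High and that the billing share is equal across arms.

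Because Section 11.2.3 lists adherence as a primary outcome variable of Aim 2, a reader might infer that the trial's main result is at risk. It is not. Section 11.1 makes Aim 2 the secondary aim, and Section 3.1.1 sets any contraceptive use as the primary outcome. The other Aim 2 outcome, continuity of use, comes from survey items and is unaffected.

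**What to change.** In the DMPA entry of Table 3 and in the text of Section 11.2.3.2, compute DMPA coverage from pharmacy and medical (health care utilization) claims together. Credit each injection claim with a number of days covered that the sponsor prespecifies as a measurement convention. Leave pills, patch and ring as written.

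Do not add self-report for enrolled women who report DMPA but have no claim in either source. Section 11.2.3.2 prefers claims because self-report has validated poorly, and the evidence it cites for retrospective report concerns oral contraceptives. Such a step would also treat a DMPA user without claims more leniently than a pill user without fills.

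The cost is a few extra codes in a claims extract that participants already authorise, plus a short edit to Table 3 and its text. It should be settled before the adherence data are analysed, so that no recoding is needed afterwards.
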